Appendix 2 Listing of Efficacy Parameters and Study Populations Analysed45

Appendix 3 Mayo Clinic Score46

Appendix 5 Multiple Imputation Model.....57

LIST OF ABBREVIATIONS

µg	microgram
ANCOVA	analysis of covariance
BLQ	below limit of quantification
CBC	complete blood count (test)
CI	confidence interval
CRF	case report form
CMH	Cochran-Mantel-Haenszel
CRO	contract research organization
DMC	Data Monitoring Committee
DSMB	Data Safety Monitoring Board
ECG	electrocardiogram
eCRF	electronic case report form
FCS	fully conditional specification
[REDACTED]	
ITT	intent-to-treat
LOCF	Last Observation Carried Forward
LSM	least square mean
MAR	missing at random
MCS	Mayo Clinic Score
MedDRA	Medical Dictionary for Regulatory Activities
MI	Multiple imputation
MITT	modified intent-to-treat
[REDACTED]	
MNAR	missing not at random
PGA	Physician's Global Assessment
[REDACTED]	
PMS	Partial Mayo Score
POC	Proof of concept
PRO	patient reported outcome
q.d.	once daily
QT _c	QT interval corrected for HR
SAE	serious adverse event
SAP	statistical analysis plan
SD	standard deviation
SOC	System Organ Class
TEAE	treatment-emergent adverse event
TMS	Total Mayo Score
WHODRUG	World Health Organization Drug Dictionary

1 INTRODUCTION

1.1 Objective of the Statistical Analysis Plan

This statistical analysis plan (SAP) provides the statistical rationale and methods that will be applied to data gathered in clinical trial Protocol No.APD334-003¹ in order to assess the safety and efficacy of APD334 in patients with moderately to severely active ulcerative colitis. Section 9 of this SAP discusses the changes in the planned analysis from the protocol. This SAP is finalized prior to database lock and data analysis start. Major changes in the analysis that are made after database lock will be documented in the Clinical Study Report with the rationales and details.

Unless otherwise noted, all statistical testing is one-sided and it is appropriate for this proof-of-concept phase 2 study to assess treatment effects of APD334 in patients with moderately to severely active ulcerative colitis.

1.2 Description of the Study and Objectives/Hypotheses

1.2.1 Summary of Study Design

APD334-003 is a phase 2, proof-of-concept and dose ranging clinical study designed to test the safety and efficacy of APD334 in patients with moderately to severely active ulcerative colitis and who have demonstrated, over the previous 5 year period, an inadequate response to, loss of response to, or intolerance of at least one of the following agents: oral 5-aminosalicylates, corticosteroids, immunosuppressives, TNF α antagonists, or integrin antagonists. Eligible patients will be randomized into a double-blind, placebo-controlled study to receive once daily (q.d.) doses of APD334 (1 mg or 2 mg) or matching placebo in a 1:1:1 ratio for 12 weeks and will be stratified by presence or absence of current oral corticosteroid usage and previous exposure to TNF α antagonists. Patients who are receiving corticosteroids at baseline must remain on the same dose for the duration of the study. No more than 50% of patients will have been previously exposed to TNF α antagonists. The trial will include adult men and women, ages 18-80 years, who have moderately to severely active ulcerative colitis (defined as a 3 component Mayo score (including the endoscopic, stool frequency, and rectal bleeding) of 4 to 9 with an endoscopic subscore of ≥ 2 and a rectal bleeding score of ≥ 1) [REDACTED]

The total study duration is approximately 18 weeks; 4 weeks for screening procedures, followed by 12 weeks of dosing, and a possible follow-up visit at week 14. Patients will capture daily stool frequency and rectal bleeding using an electronic device throughout the study and will return to the study at regular intervals for safety, [REDACTED], and efficacy assessments. A 34-week extension study is offered to patients who wish to continue treatment (APD334-005). Patients who choose not to participate in the extension study or who have discontinued prematurely from the study will have a 2-week follow-up visit after the last clinical visit. The schedule of procedures and visits for the study is provided in [REDACTED].

1.2.2 Efficacy Questionnaire: Mayo Clinic Score (MCS)

1.2.2.1 Complete Mayo Clinic Score (Total Mayo Score, TMS)

The complete Mayo Clinic Score is an instrument designed to measure disease activity of ulcerative colitis and consists of 4 subscores: stool frequency, rectal bleeding, findings of flexible proctosigmoidoscopy, and physician global assessment and total score ranging from 0 to 12 (see [Appendix 3](#)). Each component is scored individually on an integer scale of 0 to 3 (0=normal, 1=mild, 2=moderate, 3=severe), with higher scores indicating greater disease activity.

At Screening Visit:

The MCS will be evaluated during screening using patient diary entries within the 10 days prior to randomization and flexible proctosigmoidoscopy results within 10 days prior to randomization. The subscores for stool frequency and rectal bleeding are derived from the patient diaries. The scores from the 3 most recent days prior to the actual day of the study visit will be averaged and rounded to the nearest integer. The rounding will be applied to each subscore prior to the creation of the total score. Note that the day prior, day of and day after proctosigmoidoscopy cannot be used for patient diary entry because of the required bowel prep for the procedure. Patients who have less than 3 days of diary data during screening are not eligible for randomization. Examples of the subscore entries for eligibility and subscore derivation are provided in Table 1.

Table 1. Examples of eDiary Subscore Entries for Study Eligibility and Corresponding Subscore Derivation

Example	Diary Day											Valid Days for Calculation of Subscore	Average Subscore	Final Subscore
	-10	-9	-8	-7	-6	-5	-4	-3	-2	-1	1			
Diary #1	1	2	3	X	P	X	2	1	3	1	E	-1, -2, -3	1.66	2
Diary #2	2	2	2	3	X	P	X	M	1	3	E	-1, -2, -7	2.33	2
Diary #3	3	2	3	3	3	X	P	X	3	E		-2, -6, -7	3.00	3
Diary #4	3	0	1	X	P&E	X						-8, -9, -10	1.33	1
Diary #5	1	2	X	P&E	X							Missing	N/A	Missing
Diary #6	1	2	3	1	3	3	3	2	3	X	P&E	-2, -3, -4	2.67	3

Abbreviations: E = eligibility; M = missing; P = proctosigmoidoscopy; X = non-scoring day before and after proctosigmoidoscopy

The physician's global assessment (PGA) acknowledges the three other criteria findings of the MCS, the patient's daily record of abdominal discomfort and general sense of well-being, and other observations, such as physical findings and the patient's performance.

At Other Study Visits:

For each study visit during the study (excluding the screening/baseline visit which uses 10 prior days), stool frequency and rectal bleeding subscores will be derived from electronic patient diaries completed over the 7 days prior to a study visit. Note that the day prior, day of and day

after proctosigmoidoscopy will not be used for patient diary entry because of the required bowel prep for the procedure. These subscores will be calculated using the following rules:

1. The scores from the 3 most recent days prior to the actual day of the study visit will be averaged and rounded to the nearest integer.
2. If patient diary entries from 3 days are not available, the scores from the 2 most recent entries will be averaged and rounded to the nearest integer.
3. If less than 2 days of diary data are available, the subscore will be considered missing.

The rounding will be applied to each subscore prior to the creation of the total score. Table 2 provide examples of the subscore entries and subscore derivation.

Table 2. Examples of eDiary Subscore Entries and Corresponding Subscore Derivation

Example	Diary Day ¹							Valid Days for Calculation of Subscore	Average Subscore	Final Subscore
	-7	-6	-5	-4	-3	-2	-1			
Diary #1	1	2	3	1	0	0	3	-1, -2, -3	1.00	1
Diary #2	X	P	X	2	1	3	1	-1, -2, -3	1.66	2
Diary #3	1	2	3	X	P	X	2	-1, -5, -6,	2.33	2
Diary #4	2	M	M	1	M	M	M	-4, -7	1.5	2
Diary #5	M	M	3	M	M	M	M	Missing	N/A	Missing

¹ Days are named relative to the Day of Study Visit; Abbreviations: M = missing; P = proctosigmoidoscopy; X = non-scoring day before and after proctosigmoidoscopy

The MCS will also be evaluated at Week 12 using the Week 12 proctosigmoidoscopy and stool frequency and rectal bleeding scores completed by the patients seven days prior to the visit.

The proctosigmoidoscopy subscore is evaluated by the investigator and a blinded central reader. For analysis purposes, only the central reader results be will used and the derived Mayo Clinic Scores calculated by case report form (CRF) Health eDiary vendor will be analysed.

1.2.2.2 3-Component Mayo Clinic Score (Partial Mayo Score, PMS)

There are two 3-component Mayo Clinic Scores consisting of 3 of the 4 subscores found in the MCS.

1. PMS#1: the primary endpoint, consists of subscores for stool frequency, rectal bleeding and findings of flexible proctosigmoidoscopy.

2. 

Total score for the 3-component MCS range: 0 to 9, each component ranging from 0 to 3 (0=normal, 1=mild, 2=moderate, 3=severe). Both 3-component Mayo scores will be evaluated at baseline and Week 12.

1.2.2.3 2-Component Mayo Clinic Score

The 2-component Mayo Clinic Score consists of 2 of the 4 subscores found in the MCS (i.e. rectal bleeding and findings on endoscopy). Total score for the 2-component MCS range: 0 to 6, each component ranging from 0 to 3 (0=normal, 1=mild, 2=moderate, 3=severe). The 2-component Mayo score will be evaluated at baseline and Week 12.

1.2.3 Efficacy Questionnaire:

1.2.4 Objectives

Primary Objective: The primary objective of this proof-of-concept study is to determine the effect of treatment with APD334 in improving PMS#1, 3-component Mayo Clinic Score (score ranging from 0 to 9, including stool frequency, rectal bleeding and findings on endoscopy) at Week 12

Secondary Objectives:

- To determine the effect of treatment with APD334 on endoscopic improvement at 12 weeks
- To determine the effect of APD334 treatment on 2-component Mayo Clinic Score (rectal bleeding and findings on endoscopy) at 12 weeks
- To determine the effect of APD334 treatment Total Mayo Clinic Score at 12 weeks

Medical Rationale for Choice of Secondary Endpoints

- Endoscopic improvement of mucosal inflammation, as assessed by proctosigmoidoscopy, is a secondary endpoint for this study, and is considered a lead indicator of endoscopic mucosal healing in a proof-of-concept clinical trial. This endpoint measure is selected because colorectal mucosal inflammation is a defining, diagnostic feature of ulcerative colitis that provides direct, visual evidence of the inflammation characteristic of the disease², and a key goal in treating patients with ulcerative colitis is to control inflammation^{3,4}. Mucosal healing is considered an important treatment goal in both clinical trials and clinical practice because it is associated with improved outcomes, including sustained clinical remission, steroid-free remission, decreased rates of surgery, and fewer hospitalizations⁴. Endoscopic assessments of mucosal inflammation are encouraged by the Food and Drug Administration (FDA) according to the interim approaches to efficacy assessments described in the current Draft Guidance for Industry⁵. The European Medicines Agency (EMA) requires demonstration of treatment effects on the inflammatory process in ulcerative colitis by endoscopic assessments, as described in the Agency's Draft Guideline⁶.
- A two-component Mayo Clinic Score (selecting the "Rectal bleeding" and "Findings on flexible sigmoidoscopy" components, and omitting the "Stool frequency" and "Physician's global assessment" components as originally described⁷) is a secondary endpoint for this study. The rectal bleeding component is selected because of the clarity and ease of patients' reports of this finding on a contemporaneous basis. The findings on flexible sigmoidoscopy component is selected based on the rationale provided in the preceding paragraph. The stool frequency component is omitted because the scoring method requires patients to assess contemporaneous stool frequency in comparison to that during a previous "normal" health state, either before symptoms of ulcerative colitis began or during periods of remitted and quiescent disease. As such, the "normal" stool frequency is subject to patient recall bias. Further, the difficulties in patients' capabilities in accurately reporting numbers of stools necessitates specific instruction, as described in the FDA Guidance⁵, and which unfortunately may not be heeded or consistently followed by investigators or understood by patients. The physician's global assessment component is omitted because, per the FDA Guidance⁵, clinician-reported outcome measures cannot directly assess symptoms that are known only to the patient, and FDA encourages sponsors to develop patient-reported outcome (PRO) instruments as an ideal primary efficacy assessment tool for the treatment of ulcerative colitis⁵.

[figure not shown]
- Total Mayo Score (4-component and ranging 0 to 12), will reflect a broad examination of potential clinical improvement across four domains (stool frequency, rectal bleeding, findings on flexible proctosigmoidoscopy and physician's global assessment).

[figure not shown]
Safety Objective:

To determine the safety profile and tolerability of APD334 induction treatment

Exploratory Objectives:

- To determine the effect of treatment with APD334 in inducing clinical remission at 12 weeks
- To determine the effect of treatment with APD334 in inducing clinical response at 12 weeks
- To determine the effect of treatment with APD334 on a combination of clinical remission and clinical response reflected by a composite endpoint at 12 weeks

1.2.5 Hypotheses

1.2.5.1 Primary Hypothesis

In patients with moderately to severely active ulcerative colitis, treatment with APD334 compared with placebo will provide greater improvement in 3-component Mayo Clinic Score (consisting of subscores for stool frequency, rectal bleeding and findings of endoscopy) at 12 weeks.

1.2.5.2 Secondary Hypotheses

[figure not shown]
- In patients with moderately to severely active ulcerative colitis, treatment with APD334 compared with placebo will provide more patients that achieve endoscopic improvement at 12 weeks.
- In patients with moderately to severely active ulcerative colitis, treatment with APD334 compared with placebo will provide greater improvement in 2-component Mayo Clinic Score (consisting of rectal bleeding and findings on endoscopy) at 12 weeks.
- In patients with moderately to severely active ulcerative colitis, treatment with APD334 compared with placebo will provide greater improvement in Total Mayo Clinic Score (consisting of stool frequency, rectal bleeding, findings of flexible proctosigmoidoscopy, and physician global assessment) at 12 weeks.

2 DEMOGRAPHIC AND OTHER BASELINE CHARACTERISTICS

All baseline patient characteristics of demographic data (age, height, and weight), ulcerative colitis history, social history, medical history (abnormalities only), physical examination (abnormalities only), and concomitant medications at study entry will be listed for all patients. Demographic and baseline characteristics of the safety population will be summarized by treatment group and for the overall population. Baseline for the demographic variables will be the last pre-randomization value collected at the screening visit. Continuous variables will be summarized using number of values (n), mean, standard deviation (SD), median, minimum, and maximum. Frequencies and percentages will be reported for all categorical data. No formal statistical testing comparing treatment groups will be performed.

The following variables will be summarized by treatment group:

1. Continuous baseline demographic variables: age (years).
2. Categorical baseline demographic variables: sex (female or male), race (American Indian or Alaska Native, Asian, Black or African-American, Native Hawaiian or Other Pacific Islander, White or Caucasian, or Other) and ethnicity (Hispanic or Latino, Not Hispanic or Latino).
3. Ulcerative colitis history which include:
 - Duration of Ulcerative Colitis (in years)
 - Disease localization (Proctosigmoiditis/Left sided colitis, Pancolitis/ Extensive colitis)
 - Presence or absence of current oral corticosteroid usage at baseline
 - Inadequate responders/Lost response and/or Intolerant to corticosteroid (including duration of treatment)
 - Previous exposure to TNF α antagonists (including duration of treatment)
 - Inadequate responders/Lost response and/or Intolerant to TNF α antagonists
 - Previous exposure to immunosuppressives (including duration of treatment)
 - Inadequate responders/Lost response and/or Intolerant to immunosuppressives
 - Previous use of integrin antagonist (including duration of treatment) and response
 - Previous use of oral 5-aminosalicylates (including duration of treatment) and response
 - Baseline Disease Activity (Mayo Clinic Scores)

3 PATIENT DISPOSITION

The number of patients enrolled in the study by country and treatment group will be tabulated. Tables showing study participant accounting will be provided. Tables will indicate number of patients who were randomized into the study, the number of patients who completed treatment and/or completed the study, and the number of patients who discontinued treatment and/or discontinued study prematurely (early termination) for any of the following reasons:

- Adverse event(s)
- Patient lost to follow up
- Patient withdrawal of consent
- Investigator decision
- Sponsor decision
- Death
- Other

Protocol deviations will be listed and tabulated by subtype.

4 EFFICACY ANALYSES

4.1 Efficacy Endpoints

A table is provided in [Appendix 2](#) summarizing the efficacy variables and their analysis populations.

Primary Endpoint

Improvement of PMS#1, 3-component Mayo Clinic Score (score ranging from 0 to 9, including stool frequency, rectal bleeding and findings on endoscopy) at Week 12.

Secondary Endpoints

Secondary efficacy variables include:

[figure not shown]
- Proportion of patients who achieve endoscopic improvement at Week 12
Endoscopic improvement is defined as Mayo endoscopic subscore (using findings of flexible proctosigmoidoscopy) of ≤ 1 point.
- Improvement in 2-component Mayo score (score ranging from 0 to 6, including rectal bleeding and findings on endoscopy) at Week 12
- Improvement in Total Mayo Clinic Score (score ranging from 0 to 12, including stool frequency, rectal bleeding, findings on endoscopy and physician's global assessment) at Week 12.

[figure not shown]
Exploratory Endpoints

The exploratory efficacy endpoints are listed below:

- The trichotomous composite endpoint of clinical remission and clinical response (score ranging 0 to 2: score 2 for achieving both clinical remission and clinical response; 1 for achieving only clinical response, and 0 for achieving neither) at Week 12.
- The proportion of patients achieving clinical remission at Week 12
A patient has achieved clinical remission if he/she has:
 - an endoscopy score using flexible proctosigmoidoscopy of 0 or 1 (excluding friability) and
 - a rectal bleeding score of 0 or 1 and
 - a stool frequency score of 0 or 1 with a decrease of ≥ 1 point from baseline
- Proportion of patients who achieve clinical response at Week 12
A patient has achieved clinical response if he/she meets criteria of clinical remission defined above, or meet criteria of clinical response defined in the protocol. Clinical

response is defined as a decrease in 3-component Mayo Clinic score of ≥ 2 points and a decrease of $\geq 30\%$ with either a decrease of rectal bleeding of ≥ 1 or rectal bleeding score of 0 or 1

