9.5 Efficacy Endpoints

Primary:

- The improvement of 3-component Mayo Clinic Score (score ranging from 0 to 9, including stool frequency, rectal bleeding and findings on endoscopy) at Week 12.

[figure not shown]
Secondary:

- The trichotomous composite score of clinical remission and clinical response (score ranging 0 to 2: score 2 for achieving both clinical remission and clinical response; 1 for only achieving clinical response, and 0 for achieving neither) at Week 12.
- The proportion of patients achieving clinical remission [defined as individual subscores of the 3-component Mayo Clinic score as follows: an endoscopy score (using flexible proctosigmoidoscopy) of 0 or 1, a rectal bleeding score of 0, and a stool frequency score of 0 or 1 with a decrease of ≥ 1 point from baseline subscore at Week 12]
- The proportion of patients who achieve clinical response [defined as a decrease in 3-component Mayo Clinic score of ≥ 2 points and a decrease of $\geq 30\%$ with either a decrease of rectal bleeding of ≥ 1 or rectal bleeding score of 0 or 1] at Week 12

- The proportion of patients who achieve endoscopic improvement [defined as Mayo endoscopic subscore (using findings of flexible proctosigmoidoscopy) of ≤ 1 point] at Week 12

Exploratory:

- Improvement in Total Mayo Clinic Score (score ranging from 0 to 12, including stool frequency, rectal bleeding and findings on endoscopy, and physician's global assessment) at Week 12

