6.3 Multiplicity

Primary comparison is between APD334 2 mg vs placebo [REDACTED]

The primary analysis will compare PMS#1 change from baseline between treatment groups using a one-sided test at the 0.05 level of significance and 90% CI will be reported. If the result is significant, the primary hypothesis will be considered satisfied and this study will be declared positive. If this primary test is significant the secondary testing will proceed as following.

[figure not shown]
Secondary endpoints:

1. Proportion of patients who achieve endoscopic improvement at Week 12
2. Improvement in 2 component Mayo score (score ranging from 0 to 6, including rectal bleeding and findings on endoscopy) at Week 12
3. Improvement in Total Mayo Clinic Score (score ranging from 0 to 12, including stool frequency, rectal bleeding and findings on endoscopy, and physician's global assessment) at Week 12.

If the primary testing is significant, testing for secondary endpoints will proceed in pre-specified order. Provided that all previously specified tests are statistically significant ($p < 0.05$), each of these comparisons will be assessed using the one-sided test at the 0.05 level of significance. However, if a comparison is not statistically significant, then subsequent comparison(s) will be considered exploratory.

Exploratory endpoints:

- The trichotomous composite endpoint of clinical remission and clinical response (score ranging 0 to 2: score 2 for achieving both clinical remission and clinical response; 1 for achieving only clinical response, and 0 for achieving neither) at Week 12.
- The proportion of patients achieving clinical remission at Week 12
- Proportion of patients who achieve clinical response at Week 12

Non-formal statistical testing on treatment effect will be performed and reported along with nominal p-values.

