9 CHANGES IN THE PLANNED ANALYSIS FROM THE PROTOCOL

[figure not shown]
The following secondary objective and endpoint have been added to the SAP in comparison with Protocol Amendment #6:

1. 2-Component Mayo Clinic Score

The following changes to the secondary objectives and endpoints have been made:

1. The order has been changed to: Endoscopic Improvement, 2-Component Mayo Score and Total Mayo Score
2. Other objectives/endpoints previously listed as secondary (i.e. Trichotomous score, Clinical remission and Clinical response) are considered to be exploratory

The following exploratory objectives and endpoints have been added to the SAP in comparison with Protocol Amendment #6:

In addition, a change to the sample size calculation in comparison with Protocol Amendment #6 has been made:

Rationale for sample size calculation change:

In Protocol Amendment 06, the primary objective was changed to reflect a broad examination of potential clinical improvement across three domains (stool frequency, rectal bleeding, and endoscopic results), which is appropriate for a proof-of-concept study. The current endpoint is more sensitive to detecting clinically important differences between two doses of APD334 and placebo compared to a dichotomous complete remission endpoint.

The 95% CIs have been changed to 90% CIs for all analyses in comparison with Protocol Amendment #6.

The clinical remission definition has been updated to include “a rectal bleeding score of 0 or 1” in comparison with Protocol Amendment #6.

The clinical response definition has been updated as “a patient has achieved clinical response if he/she meets criteria of clinical remission, or meet criteria of clinical response defined in the protocol.”

The following change to the primary efficacy analysis has been made:

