Appendix 3 Mayo Clinic Score

Mayo Scoring System for Assessment of Ulcerative Colitis Activity³

Stool Frequency†

- 0 = Normal number of stools for this patient
 - 1 = 1–2 stools more than normal
 - 2 = 3–4 stools more than normal
 - 3 = 5 or more stools more than normal
- Subscore, 0 to 3

Rectal bleeding‡

- 0 = No blood seen
 - 1 = Streaks of blood with stool less than half the time
 - 2 = Obvious blood with stool most of the time
 - 3 = Blood alone passes
- Subscore, 0 to 3

Findings on endoscopy†

- 0 = Normal or inactive disease
 - 1 = Mild disease (erythema, decreased vascular pattern)
 - 2 = Moderate disease (marked erythema, lack of vascular pattern, friability, erosions)
 - 3 = Severe disease (spontaneous bleeding, ulceration)
- Subscore, 0 to 3

Physician's Global Assessment§

[figure not shown]
- 0 = Normal
 - 1 = Mild disease
 - 2 = Moderate disease
 - 3 = Severe disease
- Subscore, 0 to 3

† Each patient serves as his or her own control to establish the degree of abnormality of the stool frequency.

‡ The daily bleeding score represents the most severe bleeding of the day.

§ The physician's global assessment acknowledges the three other criteria, the patient's daily recollection of abdominal discomfort and general sense of well-being, and other observations, such as physical findings and the patient's performance status.

Note: The Mayo score ranges from 0 to 12, with higher scores indicating more severe disease.⁴

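### SAP 4.1 loosens clinical remission from rectal bleeding 0 to 0 or 1, so a patient whose bleeding stays at 1 can count as in remission if endoscopy and stool frequency meet their parts

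*SAP*

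**What the plan says.** Protocol 9.5 makes clinical remission a three-part rule on Week 12 subscores: endoscopy 0 or 1, then "a rectal bleeding score of 0, and a stool frequency score of 0 or 1", with stool frequency also down by at least a point from baseline. The protocol synopsis and Study Definitions carry the same rule.

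SAP 4.1 keeps the name and the three-part form, but its bleeding line reads "a rectal bleeding score of 0 or 1 and". A fall from baseline is still required only for stool frequency.

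SAP Section 9 acknowledges the difference from Amendment 06: "The clinical remission definition has been updated to include" a bleeding score of 0 or 1. No reason follows in the readable text, and parts of that section are redacted.

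Three other places in the SAP bear on the point:

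- Section 1.2.1 sets the entry floor at "a rectal bleeding score of ≥ 1".
- Appendix 3 describes a bleeding score of 1 as "Streaks of blood with stool less than half the time".
- Section 6.3 puts remission and the trichotomous score among the exploratory endpoints: "Non-formal statistical testing on treatment effect will be performed and reported along with nominal p-values".

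**The concern.** Bleeding of 1 is both the lowest score at which a patient can enter and a score at which the SAP now allows remission. With no fall in bleeding required, a patient can enter with visible blood, finish with the same amount, and be counted as in remission.

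For that patient the only patient-reported improvement required is in stool frequency. This sits awkwardly with the SAP's own view of the two items. In explaining the 2-component score, SAP 1.2.4 says "The rectal bleeding component is selected because of the clarity and ease of" patient reporting, and says that the normal "stool frequency is subject to patient recall bias". The item that was loosened is the one the SAP regards as better reported.

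What is at stake is the meaning of a reported result. Protocol and SAP describe the remission objective in the same terms but apply different rules. The 10% and 28% remission rates in Protocol 9.2 were set when remission meant bleeding 0. A rate produced under SAP 4.1 is not comparable with them, although it has the same name.

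**Working it through.** **The plan's own figures.** Protocol 9.2 is the only planned figure tied to remission: 10% against 28%, about 80 per group, two-sided 5%, 80% power. Summing Bin(a; 80, 0.10) × Bin(b; 80, 0.28) over all outcomes with Fisher's exact p ≤ 0.05 gives 79.5%. The continuity-corrected chi-square gives 78.7% and the uncorrected test 83.3%. The stated 80% is reproduced.

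SAP 7.1 is sized on the primary score: n = 2 × (1.645 + 0.842)² × 2.03² / 1.15² = 38.5, so 39 per group, as stated.

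**The two rules side by side**

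| Week 12 requirement | Protocol 9.5 | SAP 4.1 |
|---|---|---|
| Endoscopy | 0 or 1 | 0 or 1, without friability |
| Rectal bleeding | 0 | 0 or 1 |
| Stool frequency | 0 or 1, down by ≥ 1 | 0 or 1, down by ≥ 1 |

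The friability wording does not alter the scores used here, because Appendix 3 already places friability at endoscopy score 2.

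**One worked case**, written as (stool, bleeding, endoscopy). Baseline (1,1,2) totals 4 and is eligible under SAP 1.2.1. Week 12 (0,1,1) has endoscopy 1, stool down by 1 to 0, and bleeding unchanged at 1. It is remission under the SAP and not under the protocol.

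**All cases.** Eligible baselines have stool 0–3, bleeding 1–3, endoscopy 2–3 and total 4–9. There are 23: five with stool 0 and six each with stool 1, 2 and 3. Each is paired with the 4 × 4 × 4 = 64 possible Week 12 score sets.

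- Protocol remission: a baseline with stool 1 can end only at stool 0; one with stool 2 or 3 can end at 0 or 1. With two endoscopy outcomes and one bleeding outcome, this gives 6×2×1 + 6×2×2 + 6×2×2 = 60 combinations.
- SAP remission: two bleeding outcomes instead of one, so 120. The 60 added all end at bleeding 1.
- Bleeding 1 at both visits: 20 of those 60. They come from six of the seven eligible baselines with bleeding 1. The seventh, (0,1,3), fails because stool frequency cannot fall from 0.

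These counts test the logic. They are not patient frequencies.

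**Effect on other endpoints.** The protocol response rule needs a fall of at least 2 points and at least 30% in the 3-component score, plus a bleeding condition that a Week 12 score of 0 or 1 satisfies. Among SAP remissions the smallest fall is 2 points and the smallest percentage fall is 40%, for example (2,1,2) to (1,1,1), or 5 to 3. None of the 120 combinations fails the response rule. So:

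- the response rate is unchanged, even though SAP 4.1 counts remission as response;
- every reclassified patient moves from trichotomous score 1 to 2, never from 0.

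**Size per patient.** One patient is 100/39 = 2.6 percentage points of an arm at the SAP's evaluable size, or 100/80 = 1.25 points at the protocol's. If one to four patients in an arm were affected, which is an assumption, the shift would be 2.6 to 10.3 points (4/39) at 39 per group.

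**The case against.** The change is declared in SAP Section 9, and SAP 1.1 says the plan is final before database lock, so this is neither hidden nor post hoc. The endpoints concerned are exploratory with nominal p-values, and the same rule applies to every arm of a blinded trial. A patient with unchanged bleeding must still improve on a blinded central endoscopy reading from at least 2 to at most 1. The recall-bias remark in SAP 1.2.4 was written to justify the 2-component score, not the remission rule. All of this is correct, and it limits how serious the point is.

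The size is also open to challenge. The one-to-four range has no source in the documents, and 39 is the evaluable count for the primary endpoint, not necessarily the denominator for remission. Allowing for the roughly 10% missing endoscopy expected in SAP Section 9 gives 117/0.9 = 130 patients, or 43.3 per arm. Each patient is then 2.3 points and four are 9.2. The picture is much the same.

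Redaction matters too. SAP 7.4.2 is unreadable and parts of Sections 4.3.3, 7.4.1 and 9 are blacked out, so a reason or a bleeding-0 analysis may exist there. If so, the sponsor can cite it. The result named clinical remission in SAP 4.1, and score 2 of the trichotomous endpoint, would still follow the looser rule.

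**Conclusion.** The concern holds. SAP 4.1 applies the protocol's term to a weaker condition, under which unchanged visible bleeding is compatible with remission. The effect is confined to the exploratory remission rate and the split between scores 1 and 2 of the trichotomous endpoint. The primary test, the ordered secondary tests and the response rate do not depend on it.

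The total effect cannot be derived, because the documents do not say how many patients will end at bleeding 1 while meeting the other two parts. An arm's remission rate can only stay the same or rise; the effect on the treatment difference could go either way. The logic check assumes integer subscores and baselines that meet the SAP 1.2.1 entry scores. The point should be corrected, but it does not threaten the trial's main conclusion.

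**What to change.** In SAP 4.1, restore rectal bleeding 0 as the definition of clinical remission and derive the trichotomous score from it. Report the 0-or-1 version as a supplementary result under a different name, and amend Section 9 to match. If redacted text already contains a bleeding-0 analysis, move it into 4.1 under the protocol's name.

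The cost is one extra derived variable and a wording change. The downside for the sponsor is that the rate reported as clinical remission will be the same or lower. No information is lost, since both versions are reported.
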